6.2 Secondary objectives

6.2.1 Variables

Secondary variables for this study are:

- Steroid use (mg days): Change from baseline in steroid usage as determined by the investigator's decision (for any reason algorithm mediated or just related to an investigator's decision).
- - Dose for subjects dosed with Methylprednisolone steroid doses of 4, 6, 8, 10 mg will be multiplied by 1.25 to become Prednisolone equivalent.
- Composite index of pulmonary physiology and exercise capacity: Subject who deteriorates from baseline to each visit/Week 16, is defined as a subject with:
 - o relative reduction if FVC \geq 10%, or
 - o relative reduction if FEV1 \geq 10%, or

- o relative reduction of DLCO \geq 15%, or
- o relative reduction of 6MWD \geq 50 m.
- [18F]FDG-PET/CT: Percent change from baseline in SUVmax and SUVmean
- Pulmonary function tests: Change from baseline in FVC (L), FEV1 (L and % predicted), FEV1/FVC, PEF and DLCO (absolute values and % predicted). DLCO expressed as % predicted and adjusted for Hemoglobin will be derived by the vendor as described in: Graham et others 2017. A composite physiological index (CPI) will be derived too following this formula: CPI = 91 0.65*DLCO(%) 0.53*FVC(%) + 0.34*FEV1(%)
- 6MWD: Change from baseline in distance walked and for the distance saturation product. The latter will be derived as the product between the distance walked and lowest oxygen saturation (SpO2%) value observed during the test, that is to say the lowest of the values taken after 1,2,3,4,5,6 Minutes from the start of the test (Lettieri 2006).
- IL-18 and IL-18bp concentrations

The direction of benefit is as follows

- an increase in values is beneficial for: absolute FVC, FEV1, PEF, DLCO and 6MWD.
- A decrease in values is beneficial for: [18F]FDG-PET/CT (SUVmax and SUVmean).

[18F]FDG-PET/CT

The [18F]FDG-PET/CT imaging data will be analyzed by the vendor to identify the standardized uptake values in the following categories:

- A maximum of 10 focal nodal uptake regions (mediastinal, hilar)
- A maximum of 10 focal regions of uptake in lung parenchyma
- A maximum of 10 extra-thoracic focal uptake regions on the whole body scan

[18F]FDG-PET/CT mean uptake in the reference tissue:

- Lung parenchyma, unaffected by focal lesion uptake
- Ascending aorta blood pool

During the statistical analysis, for each category, a mean of the SUVmax values over the different regions from baseline and Week 16 scans will be derived. For each region a percent change at week 16 vs the initial scan, will be derived and averaged within each category too. The mean percent change represents the main endpoint for this analysis.

SUVmean values will be managed in the same way.

6.2.2 Descriptive analyses

All secondary variables will be listed by treatment, subject and visit/time. Descriptive statistics will be provided by treatment and visit/time for all continuous variables. Summary statistics will include arithmetic mean, SD, CV (arithmetic), median, minimum and maximum. Summary statistics for ancillary data (oxygen saturation, and vital signs data) collected during the 6 minute walking test will be provided too.

Il-18 and IL-18bp concentrations will be listed and summarized by treatment producing outputs mirroring the ones provided for the PK analysis of CMK389 concentrations but including the results observed in the placebo group.

Clinical status evaluation data (see section 3.1 of the study protocol) will be listed and summarized by treatment and visit. The summary table will report for each component (6MWT distance, FVC, FEV1, MMRC dyspnea score) the corresponding evaluation (Better, Same, Worse) and the overall evaluation.

Subjects who deteriorate at Weeks 4, 8, 12 and 16 and subjects with any increase in steroids for any reason (algorithm driven or not) during the treatment epoch will be summarized, separately, by treatment group using frequency tables.

The correlation between percent changes from baseline [18F]-FDG-PET/CT scan in SUVmax and changes from baseline in FVC, FEV1 and 6MWT distance will be assessed with scatterplot grids. As we may not be able to assume normality of the data, Kendall's tau-b coefficients and its corresponding p-values will be displayed to assess correlation.

Data on new lesions from [18F]-FDG-PET/CT will be only listed.

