# 11.5 Analysis of secondary variable(s)

#### 11.5.1 Efficacy / Pharmacodynamics

Data from other secondary variables will be listed and summarized. Graphical representations over time will be presented. Models similar to the one described for the primary analyses will be carried-out to investigate treatment difference for the continuous variables collected at each visit of the treatment epoch. Pulmonary physiology scores will be analyzed via ANCOVA model for repeated measures, while the percentage of subjects that, at Week 16, deteriorate (defined as: relative reduction from baseline in FVC  $\geq 10\%$  or in FEV1  $\geq 10\%$  or in DLCO  $\geq 15\%$  or relative of 6MWD  $\geq 50$  m) and the percentage of subjects who increased the steroid dose at least one time during the treatment epoch, will be analyzed using logistic regression. This analysis will be carried out if at least 20% of the subjects will show a deterioration/increase of the steroid dose.

The [F]FDG-PET/CT imaging data will be analyzed to identify the maximum standardized uptake values in the following categories:

• A maximum of 10 focal nodal uptake regions (mediastinal, hilar)

Page 84

- A maximum of 10 focal regions of uptake in lung parenchyma •
- A maximum of 10 extra-thoracic focal uptake regions on the whole body scan ٠

F]FDG-PET/CT mean uptake in the reference tissue:

• A region of lung parenchyma, unaffected by focal lesion uptake

The mean of the SUVmax (resp. SUVmean) for each category will be taken to obtain one SUVmax value (resp. SUVmean) per patient / time point / category.

The mean percent change from baseline in SUVmax in the lymph nodes after 16 weeks of treatment will be analyzed using ANCOVA with baseline SUVmax and baseline steroid doses as covariates, and treatment and prior sarcoidosis immunosuppressant therapy as factors.

The same analysis as for the percent change from baseline in SUVmax in the lymph nodes will be performed for the percent change from baseline in SUVmax in the lung parenchyma and the extra-thoracic regions, where available. It will also be repeated for SUV mean in the parenchyma.

The correlation between changes from initial FDG-PET scan in SUVmax and changes from baseline in FVC, FEV1 and 6MWT distance will be assessed with graphical methods.

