6.1.5 Sensitivity/Supplementary analyses

Supplementary analyses may be conducted including also FVC values collected after a change of the background therapy driven by the algorithm or not.

Finally the analysis may be repeated excluding the observations with flags related to data quality (REIRESFL='Y').

A scatterplot will be produced to investigate the relationship between week 16 FVC changes from baseline and SUV max % changes

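### SAP 6.2.2 does not say whether Kendall's tau-b between PET change and lung-function change is pooled or by arm; if pooled, a treatment effect on both can create correlation that is absent within arms

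*SAP*

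**What the plan says.** Protocol 11.5.1 plans a purely visual assessment: the link between SUVmax change and "changes from baseline in FVC, FEV1 and 6MWT distance will be assessed with graphical methods". No coefficient or p-value appears there.

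SAP 6.2.2 keeps the plots, saying that SUVmax percent change and "changes from baseline in FVC, FEV1 and 6MWT distance will be assessed with scatterplot grids". Because normality may not hold, it adds that Kendall's "tau-b coefficients and its corresponding p-values will be displayed to assess correlation". It names no arm, stratification, treatment adjustment, significance level or decision rule.

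Other items in 6.2.2 do state their grouping. For example, "Descriptive statistics will be provided by treatment and visit/time for all continuous variables", and deteriorations and steroid increases "will be summarized, separately, by treatment group using frequency tables". SAP 6.1.5 has a related plot that is also silent on arm: "A scatterplot will be produced to investigate the relationship between week 16 FVC changes from baseline and SUV max % changes".

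SAP section 6 opens by placing every subject in the PD analysis set into the PD analysis. With no grouping stated, the literal default is therefore one coefficient per pair of variables over both arms.

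**The concern.** SAP 6.2.1 gives opposite directions of benefit: SUV values should fall, while FVC, FEV1 and 6MWD should rise. An effective drug therefore separates the arms on both axes. A CMK389 patient compared with a placebo patient will tend to have the lower SUVmax change and the higher FVC change. Such pairs push a pooled tau-b below zero even if, within each arm, a patient's PET change says nothing about lung-function change.

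The artefact has the same sign as the association a reader hopes to see, and it grows with efficacy. Protocol 8.5.7 supports the use of PET partly by reported correlations with FVC improvement, so a small p-value here would invite the reading that PET tracks lung function in this trial. A pooled p-value cannot separate that from the drug having moved both measures.

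**Working it through.** **Inputs from the documents.** Protocol 11.7 gives 28 evaluable patients per arm (66 × 0.85 = 56.1), an SD of 9 and a true FVC effect of 5, so 5/9 = 0.556 SD.

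**Assumptions.**
- The PET effect in SD units is not given, so a range of 0.3 to 3.0 SD is used. Protocol 8.5.7 reports falls of 53–55% in two previous trials, but with no SD.
- The level is two-sided 5%, since the SAP states none.
- Data are normal, and all 56 patients have PET data.
- FVC is in percent predicted, since 6.2.2 gives no unit.
- The FEV1 and 6MWT effects are not given, so the figures below are for FVC only.

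**The plan's own figure.** Power at one-sided 10% is Φ(5 / (9 × √(2/28)) − 1.282) = Φ(2.079 − 1.282) = 0.787. This agrees with the stated approximate 80%, so the inputs are read correctly.

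**Expected pooled tau with zero within-arm correlation.** Of 56 × 55 / 2 = 1,540 pairs, 28 × 28 = 784 are between arms, a share of 0.509. Within-arm pairs contribute zero on average. For effects d_PET and d_FVC in SD units:

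E(tau) = −0.509 × [2Φ(d_PET/√2) − 1] × [2Φ(d_FVC/√2) − 1]

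At d_FVC = 0.556 the last bracket is 0.306. At d_PET = 2.0 the first is 0.843, so E(tau) = −0.509 × 0.843 × 0.306 = −0.131.

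**Critical value.** The null SE of tau is √[2(2n+5) / (9n(n−1))]. At n = 56 it is 0.092, so p < 0.05 needs |tau| above about 1.96 × 0.092 = 0.18.

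**Simulated rejection rate of the pooled test** (4,000 trials per scenario, zero within-arm correlation, FVC effect 0.556 SD):

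| PET effect (SD) | Expected tau | Pooled test, p < 0.05 |
|---|---|---|
| 0 | 0 | 4.8% |
| 0.3 | −0.026 | 5.8% |
| 0.8 | −0.067 | 10.4% and 11.5% (two sets) |
| 1.2 | −0.094 | 17.2% |
| 2.0 | −0.131 | 29.4% and 29.9% (two sets) |
| 3.0 | −0.150 | 39.2% |

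The Monte Carlo SE near 11% is √(0.11 × 0.89 / 4000) = 0.5 points, so the paired results agree. With no FVC effect, the rate is 4.2–5.2% whatever the PET effect.

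**The alternative.** The arm-stratified tau counts only within-arm pairs: 2 × 378 = 756. Its null SE is √(2 × 28 × 27 × 61 / 18) / 756 = 71.6 / 756 = 0.095. In the same simulations its rejection rate stays between 3.8% and 5.4%. At a true correlation of −0.4 its power is about 80%, against 83% for the pooled test.

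**Separate per-arm coefficients.** At n = 28 the null SE is 0.134, and 0.134 / 0.092 = 1.46. Each arm's coefficient is thus about 46% less precise than a pooled one, and |tau| must exceed about 1.96 × 0.134 = 0.26 for p < 0.05.

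**The case against.** The strongest reply is that pooling is inferred from silence. The SAP omits arm wording elsewhere, for example for the spirometry boxplots (6.1.2) and the PET bar chart (6.2.3). SAP 1.1 leaves presentation to separate table and figure shells that are not public and may settle the grouping. This stands: the documents support that the grouping is not stated, not that a pooled analysis was chosen.

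A reader might also infer that a treatment effect on both measures is by itself enough to yield a significant correlation. The figures do not support that. At the planned FVC effect most simulated trials do not reach p < 0.05. Rates above one half need effects well beyond plan: an FVC effect of 1.0 SD, which is 9 points against the planned 5, with a PET effect of 1.5 SD gives about 55%.

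It is also fair that the item sits under descriptive analyses in a non-confirmatory study, has no threshold or decision rule, and serves no listed primary or secondary endpoint. Nor is it a defect that the SAP adds a coefficient to a planned plot.

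Finally, a pooled tau-b validly tests marginal independence, and if the drug moves both measures they are marginally associated. That is correct, but that null does not address whether PET change follows lung-function change apart from treatment, which is the likely use of the result.

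**Conclusion.** The point holds as a minor one. SAP 6.2.2 leaves the grouping of tau-b open, and its literal reading is pooled. If pooled, the p-value mixes the treatment effect with any patient-level association. At the planned FVC effect the chance of p < 0.05 with no within-arm association is about 6% to 30% for PET effects of 0.3 to 2.0 SD, against a nominal 5%. There is no inflation unless the drug affects both measures.

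The size rests on the assumed PET effect, the assumed two-sided 5% level, normal data and complete PET data in 56 patients. The direction does not depend on the exact PET figure. The primary analysis, the efficacy criterion and the PET ANCOVA, which has treatment as a factor, are untouched.

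**What to change.** In SAP 6.2.2, state that any displayed p-value is based on the arm-stratified tau-b, combining within-arm pairs from both arms. Mark the arms on the scatterplots in 6.2.2 and 6.1.5, and label the p-values as descriptive. A pooled coefficient may be shown without a p-value.

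No new data are needed; this takes a sentence or two and a small programming change. The stratified tau loses about 2 to 3 points of power relative to the pooled one. If separate per-arm coefficients are also shown, their lower precision should be noted beside them.

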6.2.3 Statistical model, assumptions and hypotheses

[¹⁸F]-FDG-PET/CT

The mean percent change from baseline in SUVmax in the nodules and lung parenchyma at week 16 will be analyzed using ANCOVA with baseline SUVmax and baseline steroid doses as covariates and treatment and prior sarcoidosis immunosuppressant therapy as factors.

The same analysis as for the percent change from baseline in mean SUVmax in the nodules and lung parenchyma will be performed for the percent change from baseline in SUVmax in extrathoracic regions, where available, at week 16. It will also be repeated for SUVmean in the three categories.

The same sensitivity and subgroup analyses as the primary may also be performed, if deemed necessary.

A bar chart plot of the percent change from baseline with the corresponding SE will be provided.

Composite index of pulmonary physiology and exercise capacity /steroid dose

A logistic regression model with baseline steroid doses as a covariate and treatment and prior sarcoidosis immunosuppressant therapy as factors, will be applied to patients showing at least a deterioration (as determined by Composite index of pulmonary physiology and exercise

capacity- section 6.2.1) during the treatment period and to patients with at least one steroid dose increase (for any reason - algorithm mediated or just related to an investigator's decision).

Bar chart plots representing the percentage of patients with at least a deterioration during the course of the trial/ with at least one steroid increase during the course of the trial will be provided by treatment.

Key Pulmonary function tests and 6MWD

FVC (in litres), FEV1, FEV1/FVC, PEF, DLCO, DLCO adjusted for hemoglobin, CPI, 6MWD and distance saturation product changes from baseline will be analyzed using the same analysis as defined in Section 6.1.3 but under a frequentist approach (no prior will be applied). The same sensitivity and subgroup analyses as the primary may also be performed, if deemed necessary.

Model based means with corresponding standard errors (SE) by treatment and time will be used to visualize the results over time. A change from baseline of 0 will be assumed at baseline.

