## 2.2 Secondary objective(s)

Secondary objective(s)	Endpoints related to secondary objective(s)

 
To assess the impact of CMK389 on steroid use (mg days)
 
	
 
Difference in steroid usage for each arm of the study between baseline and end of treatment
 

 
To assess the impact of CMK389 on a composite index of pulmonary physiology and exercise capacity
 
	
 
Proportion of patients who deteriorate from baseline to Week 16, defined as: relative reduction in FVC ≥ 10% or relative reduction in FEV1 ≥ 10% or relative reduction of DLCO ≥ 15% or relative reduction of 6MWD ≥ 50 m
 

Secondary objective(s)	Endpoints related to secondary objective(s)

 
To explore the impact of CMK389 observed with [F]-fluorodeoxyglucose positron emission tomography/computed tomography ([F]-FDG-PET/CT) imaging
 
	
 
Change in [F]-FDG-PET/CT (SUVmax and SUVmean) from baseline and Week 16
 

 
To assess the pharmacokinetics of

	
 
Pharmacokinetic parameters (Cmax/End of

CMK389	infusion, Ctrough) of CMK389

 
To assess the safety and tolerability of

	
 
Adverse events, vital signs and routine safety

CMK389	laboratory results.

 
To assess the impact of CMK389 on pulmonary physiology
 
	• Change in forced expiratory volume in one second (FEV1) and diffusion capacity for carbon monoxide (DLCO) between baseline and Week 16

 
To assess the impact of CMK389 on

	
 
Change in 6-minute walk distance (6MWD)

exercise capacity	between baseline and Week 16

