1.3.2. Secondary objective(s)			
Secondary objective(s)	Endpoints related to secondary objective(s)		
 To assess the impact of CMK389 on steroid use (mg days) 	Difference in steroid usage for each arm of the study between baseline and end		

of treatment.

Proportion of patients who deteriorate

from baseline to Week 16, defined as:

parameters (SUVmax and SUVmean)

relative reduction in FVC \geq 10% or relative reduction if FEV1 \geq 10% or relative reduction of DLCO \geq 15% or relative reduction of 6MWD \geq 50 m.

Change in [18F]FDG-PET/CT

between baseline and Week 16.

To assess the pharmacokinetics of CMK389	Pharmacokinetic parameters (Cmax/End of infusion, Ctrough) of CMK389.
• To assess the safety and tolerability of CMK389	Adverse events, vital signs and routine safety laboratory results.
To assess the impact of CMK389 on pulmonary physiology	Change in forced expiratory volume in one second (FEV1) and diffusion capacity for carbon monoxide (DLCO) between baseline and Week 16.
To assess the impact of CMK389 on exercise capacity	Change in 6-minute walk distance (6MWD) between baseline and Week 16.

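### SAP 6.2.3 models composite deterioration at any treatment visit, where protocol 11.5.1 plans a logistic regression of deterioration at Week 16

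*SAP*

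**What the plan says.** Protocol 11.5.1 gives two binary outcomes to logistic regression in one sentence, each with its own time frame. For the composite it is "the percentage of subjects that, at Week 16, deteriorate". For steroids it is "the percentage of subjects who increased the steroid dose at least one time during the treatment epoch". The regression is run only if at least 20% of subjects show the event.

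SAP 6.2.3 gives both outcomes the same time frame. The model "will be applied to patients showing at least a deterioration" on the composite "during the treatment period and to patients with at least one steroid dose increase". The accompanying chart shows "the percentage of patients with at least a deterioration during the course of the trial". The 20% condition does not appear there.

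The other descriptions of the composite are less specific:

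- Protocol 2.2: "Proportion of patients who deteriorate from baseline to Week 16".
- SAP 1.3.2: "from baseline to Week 16, defined as", followed by the same thresholds.
- SAP 6.2.1: "Subject who deteriorates from baseline to each visit/Week 16, is defined as a subject with" one of the listed reductions.
- SAP 6.2.2: frequency tables of deterioration by treatment at Weeks 4, 8, 12 and 16.

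**The concern.** Status at Week 16 and deterioration at any of four visits are different outcomes. A patient who meets a threshold at Week 4 but not at Week 16 is an event under SAP 6.2.3 and a non-event under protocol 11.5.1. SAP 1.1 says that the SAP implements the protocol's planned analysis, yet a programmer who follows SAP 6.2.3 exactly would produce an odds ratio for an outcome that the protocol did not plan to model. A reader of the study report would probably take that odds ratio as the result for the declared secondary endpoint.

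The choice can also decide whether a model is fitted at all. At-least-once scoring can only raise the event rate, so a 20% threshold is easier to reach.

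**Working it through.** **Comparison of the texts**

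| Place | Composite | Steroid increase |
|---|---|---|
| Protocol 2.2 | baseline to Week 16 | not stated as a proportion |
| Protocol 11.5.1 (model) | at Week 16 | at least once in treatment |
| SAP 1.3.2 | baseline to Week 16 | not stated as a proportion |
| SAP 6.2.1 | each visit and Week 16 | not stated as a proportion |
| SAP 6.2.2 (tables) | each of Weeks 4, 8, 12, 16 | any increase in treatment |
| SAP 6.2.3 (model, chart) | at least once | at least once |

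The direct conflict is between protocol 11.5.1 and SAP 6.2.3. Because 11.5.1 uses both time frames in one sentence, its Week 16 wording for the composite is unlikely to be loose drafting. The baseline-to-Week-16 phrase fits that reading but, taken alone, could mean the interval. SAP 6.2.1 does not say which version is modelled.

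**The plan's own figures**

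None concerns the composite; protocol 11.8 gives no power for secondary variables. The primary figures in protocol 11.7 reproduce. With 28 per arm, SD 9, difference 5 and one-sided 0.10, power is Φ(5 / (9 × √(2/28)) − 1.282) = 0.787, against about 80% stated. For size, 56 / 0.85 = 65.9, so 66. The planned share without Week 16 FVC is 1 − 56/66 = 0.152.

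**How far apart the two outcomes could be (illustration)**

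The assumptions are mine, not the documents': the same event rate p at Weeks 4, 8, 12 and 16, a latent normal variable with equal correlation r between visits, no steroid titration and no treatment effect. With c = Φ⁻¹(p),

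at-least-once rate = 1 − ∫ φ(u) × [1 − Φ((c − √r·u) / √(1 − r))]⁴ du.

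| Week 16 rate p | r = 0.9 | r = 0.7 | r = 0.5 | r = 0.3 |
|---|---|---|---|---|
| 0.10 | 0.163 | 0.217 | 0.259 | 0.295 |
| 0.20 | 0.298 | 0.380 | 0.444 | 0.503 |
| 0.30 | 0.419 | 0.516 | 0.590 | 0.658 |

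At p = 0.20, the share of modelled events that are not Week 16 events is 1 − 0.20/0.298 = 0.33 at r = 0.9 and 1 − 0.20/0.503 = 0.60 at r = 0.3.

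**The 20% condition**

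At p = 0.10, the protocol's condition fails on the Week 16 rate. On the at-least-once rate it still fails at r = 0.9 (0.163) but passes at r = 0.7 or lower (0.217 and above).

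**Whether the treatment estimate can differ**

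Take one assumed late-onset pattern: placebo 30% at every visit; active 30%, 25%, 20% and 15%. The Week 16 odds ratio is (0.15/0.85) / (0.30/0.70) = 0.41. For at-least-once it is 0.68 at r = 0.5 and 0.71 at r = 0.7. An early effect that fades would shift the comparison the other way. The example shows only that the two estimates need not agree.

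**The case against.** The strongest defence is that little is lost. The declared endpoint is a proportion, and SAP 6.2.2 tabulates the Week 16 proportion by arm. The protocol's model was itself conditional: at a true 10% rate it would not have been planned at all. At-least-once scoring also keeps early events in patients who later lose Week 16 data. The study is non-confirmatory, and no power is claimed for secondary variables. All of this stands, and it limits the weight of the point. It does not explain why the SAP models another outcome without saying so.

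Several stronger readings are tempting, but the documents do not support them:

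- **Every definition says Week 16.** Only protocol 11.5.1 says so explicitly.
- **The Week 16 result disappears.** It remains in the frequency tables; only the modelled comparison goes.
- **The model is fitted only to patients with events.** SAP 6.2.3 can be read that way, but such a model would have no outcome variation, and SAP 6 puts all PD-set subjects into the PD analysis. This is loose wording.
- **A missing-component rule was forgotten.** None is visible, but SAP 1.1 assigns derived-variable specifications to a separate programming document that is not available here.
- **Dropout seriously biases the at-least-once outcome.** At p = 0.20, if the whole 15.2% left after Week 4, an arm's rate would fall by 0.152 × (0.298 − 0.20) = 1.5 points to 0.152 × (0.503 − 0.20) = 4.6 points. This largely cancels if dropout is balanced.

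One argument for at-least-once scoring is also weaker than it looks: that steroid increases let patients worsen and then recover. Titration follows the clinical status determination in protocol Figure 3-2. That needs two worse parameters or a two-point dyspnea change, with a 15% FVC or FEV1 fall since Day -42. The composite needs any one component, with a 10% FVC or FEV1 fall from baseline. A composite deteriorator can therefore be classed as stable and have the dose lowered, so the argument covers only a subset.

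**Conclusion.** The mismatch is real and rests on plain text. Protocol 11.5.1 plans to model Week 16 deterioration, and SAP 6.2.3 models and charts deterioration at any time, without a reason and without the 20% condition. What is lost is the planned, conditional, model-based treatment comparison for Week 16 status.

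The size cannot be derived from the documents. The illustrative rates depend on the assumed visit rates and correlations, and they ignore titration, which is part of the design. The effect on power, and the direction of any change in the treatment estimate, are undetermined.

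This is a minor-to-moderate correction. It concerns a secondary endpoint in a non-confirmatory study whose efficacy criterion uses FVC only.

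**What to change.** In SAP 6.2.3, make deterioration at Week 16 the outcome of the logistic model and the bar chart. Restate protocol 11.5.1's 20% condition and apply it to the Week 16 rate. Keep at-least-once deterioration as a labelled supplementary analysis. The steroid-increase outcome can stay as it is. If the sponsor prefers at-least-once as the main modelled outcome, the SAP should say that this departs from the protocol, and why.

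The cost is SAP wording and some programming, with no new data. The downside is that patients without usable Week 16 data contribute no Week 16 status, while at-least-once scoring keeps their earlier events. They include the roughly 15% planned dropout and patients whose later data are excluded after background-therapy changes outside the algorithm (SAP 4 and 6.1.1). Report their number by arm.

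As an assumed example for dropout alone, take 6 events among 28 observed of 33 in an arm. The observed rate is 6/28 = 21%. Over all 33 it lies between 6/33 = 18% (no missing patient deteriorated) and (6 + 5)/33 = 33% (all did). Further exclusions would widen that range.
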